## 7.5.2.1.2 Cohort D

Identification of somatic mutations in the blood will be confirmed by sequencing of the resected tumor using a CLIA-certified next-generation sequencing panel at MD Anderson. Clearance of ctDNA will be characterized by the disappearance of all somatic mutations identified in the blood, as well as no appearance of any additional new somatic mutations following 6 doses of M7824. For this cohort, we will estimate the response rate as the percentage of patients whose ctDNA status converts from "positive" to "negative" after twelve weeks of therapy with M7824 relative to the total number of patients treated.

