jTumor measurements should occur with CT imaging or MRI. Ideally the same methodology would be used over the course of the study for a given patient. Bone scan should be done at screening if clinically indicated. For collection of those prior imaging studies prior to informed consent, readily available imaging studies since the onset of metastatic/unresectable disease are to be prioritized for collection. If the results of a CT scan or MRI performed within 4 weeks prior to first treatment are available, the screening CT and/or MRI does not need to be performed.

kTumor measurements are to be assessed every 12 weeks (+/- 5 days). For subjects continuing treatment beyond 12 months, tumor evaluations should take place every 12 weeks (+/- 5 days).

To be performed on archival tissue or fresh biopsy either via hotspot next general sequencing panel in CLIA certified molecular diagnostics laboratory at MD Anderson. TGFβR2, ACVR2A, SMAD2 and SMAD4 will need to be performed if not done previously. mPlasma will be sent for markers including, but not limited to, interleukin (IL) IL-1α, IL-1β, IL-2, IL-5, IL-6, IL-8, IL-13, TNF-α, MCP, MIP-1β, G-CSF, GM-CSF, IFN-γ via a cytokine assay ((Meso Scale Discovery (MSD), 40 Plex). Leukocyte subpopulations and

immune activation status will be assessed by flow cytometry (fluorescence-activated cell sorter [FACS]) on PBMC from heparinized blood samples (10 mL, tubes).

nPD-L1 expression by immunohistochemistry on archival tumor specimen or fresh tumor tissue (if available).

oOne 10 mL vial of blood will be drawn prior to M7824 infusion and immediately following completion of M7824 infusion for doses 1 and 3 (cycle 1 day 1 and cycle 2 day 1) for analysis of pharmacokinetics. One 10 mL vial of blood will be drawn prior to M7824 infusion of M7824 infusion for doses 2 (cycle 1 day 15) and dose 6/end of treatment (whichever comes first). Refer to Section 6.4.3 for details on processing of PK samples.

pβ-hCG (no FSH) at post-progression follow-up visit

qWindow of +/- 7 days is allowed

rAdverse events are recorded and assessed continuously throughout the trial (see Section 6.4.1.3) and are assessed for final outcome at the End of Treatment visit. After the End of Treatment visit only AEs that are deemed attributable to trial drug by the Investigator should be documented until the Safety Follow-up visit.

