- 14. **Highly** effective contraception for both male and female subjects if the risk of conception exists. **Highly** effective contraception must be used 30 days prior to first trial administration, for the duration of trial treatment, and at least for 4 months after stopping trial treatment (see Appendix 2 for further details). Should a woman become pregnant or suspect she is pregnant while she or her partner is participating in this trial, the treating physician should be informed immediately.
- 15. Ability to tolerate receipt of radiotherapy to a metastasis not adjacent to a normal doselimiting structure, at the discretion of the treating radiation oncologist (cohort B).
- 16. Presence of detectable ctDNA following completion of R0 resection with or without perioperative therapy (cohort D only).
- 17. Completion of all standard-of-care adjuvant therapy (cohort D).

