### 6.2.8 ctDNA testing

Guardant360 is a next-generation sequencing (NGS) panel of 70 clinically actionable onco- and tumor suppressor genes utilizing digital sequencing of cell-free circulating tumor DNA (cfDNA) isolated from a simple, non-invasive blood draw. It is medically indicated for the prevention of a repeat invasive biopsy in advanced cancer patients when the initial biopsy is insufficient (QNS) or unavailable/unobtainable as well as when cancer has progressed or recurred despite treatment. The test detects single nucleotide variants via complete exon sequencing in 70 genes, copy number

amplifications in 16 genes, small indels in EGFR, ERBB2 and MET exon 14 skipping, and fusions in ALK, FGFR2, FGFR3, RET, ROS1 and NTRK1. The genes are selected because mutations in these genes have FDA-approved matched therapies or are eligible for late phase clinical trials, as well as non-druggable genes with high prevalence alterations that may be helpful in monitoring for molecular response/non-response such as TP53.

Guardant360 is an advanced diagnostic laboratory test (ADLT) offered by a sole source laboratory certified by the Clinical Laboratory Improvement Amendments (CLIA) for high complexity (molecular pathology) testing and accredited by the College of American Pathology (CAP). Due to high rates of false positives with traditional NGS assays when tumor DNA is in low concentrations, the majority of "liquid biopsy" methods interrogating cell-free DNA have been limited to hotspot analyses. In contrast, the ultra-high specificity (> 99.9999%) of the digital sequencing method enables the sequencing of long, targeted regions (146,000 base pairs) without false positives. Complete exons are sequenced for all exons in 30 genes and the critical exons (those reported as having a somatic mutation in COSMIC) in 40 additional genes. Thus, its key differentiating characteristic from other "liquid biopsy" methods is the ability to sequence complete exons in many genes, in contrast to gene hotspot testing.

Advantages of the Guardant360 cell-free DNA NGS methodology versus solid tumor tissue-based NGS are:

- 1. An invasive needle or surgical biopsy is avoided with ctDNA, reducing costs and complications.

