#### Methodology

The gene panel was selected to focus on those genomic alterations that are currently actionable defined as being targets of sensitivity or resistance to an FDA-approved matched therapy and/or a targeted therapy in clinical trials. The test simultaneously sequences the 70 cancer-related genes to an average depth of coverage of greater than 8,000X. To summarize, cell-free DNA is extracted from plasma and genomic alterations are analyzed by massively parallel paired end synthesis-by-sequencing of amplified target genes utilizing an Illumina Next-Seq platform complemented by systematic end-to-end process optimization including conversion of cell-free DNA fragments into digital sequences, improvements in the Illumina next generation sequencing process itself, followed by bioinformatics algorithms which enable ctDNA to be measured as a quantitative percentage of total cell-free DNA.

Two 10mls of whole blood are collected in Streck Cell-Free DNA Blood Collection (Streck) tubes, which contain a proprietary formaldehyde-free preservative in that stabilizes white blood cells, preventing the release of genomic DNA and allowing shipping and stability for seven days without need for refrigeration, cold bricks or preliminary centrifugation prior to shipping.

After digital libraries are produced, the sample is sequenced and post-sequencing data is processed using bioinformatics algorithms to quantify the absolute number of unique DNA fragments at a given nucleotide position. This proprietary process is referred to as Digital SequencingTM and enables reporting of the fractional concentration (mutant allele frequency) of a given SNV. Circulating cell-free DNA is mostly derived from leukocyte lysis (germline) and generally a much smaller amount of tumor DNA is derived from cancer cell apoptosis/necrosis. All of the cell-free DNA fragments, including leukocyte-derived and tumor-derived, are simultaneously sequenced with up to single molecule sensitivity. In other words, both tumor DNA and "normal"/germline DNA are sequenced and measured in the same sequencing assay. The fractional concentration or mutant allele frequency for a given mutation is calculated as the fraction of circulating tumor DNA harboring that mutation in a background of wild-type cell-free DNA fragments. The analytic sensitivity reaches detection of 1-2 single mutant cell-free DNA molecules from a 10 ml blood sample.

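### Cohort D: the planned tumor confirmation of blood mutations is not carried into the clearance definition, so a non-tumor somatic variant can be scored as non-clearance

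*Combined protocol and SAP*

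**What the plan says.** Section 7.5.2.1.2 has three relevant steps.

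- Confirmation: "Identification of somatic mutations in the blood will be confirmed by sequencing of the resected tumor using a CLIA-certified next-generation sequencing panel". No timing is given, and nothing is said about a blood mutation that the tumor does not show.
- Clearance: "disappearance of all somatic mutations identified in the blood, as well as no appearance of any additional new somatic mutations", judged after 6 doses.
- Estimator: patients converting from positive to negative at twelve weeks, divided by all treated patients.

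On entry, inclusion criterion 16 in Section 4.3.1 asks for "Presence of detectable ctDNA following completion of R0 resection with or without perioperative therapy (cohort D only"). Section 4.1.1.3 lets patients start treatment once a positive result is confirmed, without saying what confirms it.

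On the assay, the methodology part of Section 6.2.8 says "Circulating cell-free DNA is mostly derived from leukocyte lysis (germline"), and that leukocyte- and tumor-derived fragments are sequenced together. The same section says that the test reports germline as well as somatic variants. No paired leukocyte sequencing or other filter for tissue of origin is described.

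Section 7.1.3 sets the cohort at 15 patients, with a 95% confidence interval half-width of at most 0.253.

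**The concern.** The confirmation step has a purpose only if some blood mutations might fail it. Yet the next sentence counts all somatic mutations in the blood, and any new one, without reference to the result. A mutation that is somatic but not from tumor need not respond to tumor control. If it persists, or first appears at week 12, the literal rule makes the patient a non-clearer even when every tumor mutation has gone. A patient who is positive only through such a variant can meet criterion 16 as worded and remain in the denominator.

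The new-mutation clause is the harder part. Even if the baseline clause is read as limited to confirmed mutations, nothing ties a new week-12 mutation to tumor.

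At stake is the only primary endpoint of a 15-patient cohort. Two analysts could score the same patient differently, each in good faith.

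**Working it through.** **1. The plan's own figure.** The Wald half-width at p = 0.5, n = 15 is 1.96 × √(0.25/15) = 0.253, which matches Section 7.1.3. The exact interval named in Section 7.5.2.1.1 has a maximum half-width of 0.261 (at 7 or 8 of 15). That difference is small and is not the issue here.

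**2. Weight of one patient.** 1/15 = 6.7 percentage points.

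**3. Downward route.** Let c be the true clearance rate for tumor-confirmed mutations, and q the share of treated patients with at least one persistent or new non-tumor somatic variant, independent of tumor clearance. Under the literal rule the observed rate is c × (1 − q). The documents give neither value; c = 0.40 and the range of q are assumptions.

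| q | Observed rate, literal rule | Chance of at least 1 affected patient in 15, 1 − (1 − q)^15 |
|---|---|---|
| 0.10 | 0.40 × 0.90 = 0.36 | 0.79 |
| 0.20 | 0.40 × 0.80 = 0.32 | 0.97 |
| 0.30 | 0.40 × 0.70 = 0.28 | 0.995 |

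If only tumor-confirmed mutations count, the expected rate is 0.40 in every row.

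In counts, suppose 6 of 15 patients clear their tumor mutations (0.40, exact 95% CI 0.163 to 0.677). If two of the six carry a persistent non-tumor variant, the literal rule reports 4 of 15 (0.267, 0.078 to 0.551).

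**4. Upward route.** Let f be the share of treated patients with no tumor-derived ctDNA, and d the chance that their variant is below detection at week 12. With no other misclassification, the observed rate is c × (1 − f) + f × d. With c = 0.20, f = 0.20 and d = 0.50 (all assumed), this is 0.16 + 0.10 = 0.26, above the true 0.20. With d = 0 it is 0.16. The sign of the bias therefore depends on quantities that the documents do not give.

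**5. Can confirmation fail for technical reasons?** Section 6.2.8 presents as the blood assay's distinguishing feature its "ability to sequence complete exons in many genes, in contrast to gene hotspot testing": all exons in 30 genes and critical exons in 40 more. The Table 3 footnote on mutation profiling reads "To be performed on archival tissue or fresh biopsy either via hotspot next general sequencing panel", and Section 6.4.5 describes a 409-gene panel that sequences known hotspots. Section 7.5.2.1.2 does not say that its tumor panel is this one. A coverage mismatch is possible, and no rule covers it, but it is not shown.

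**The case against.** The best defence is that the two sentences of Section 7.5.2.1.2 should be read together, so that the mutations which must disappear are those just described as confirmed. Section 4.1.1.3 adds a requirement for a confirmed positive result, and ctDNA is defined in the abbreviations as tumor DNA. This is a fair reading, and it means that the text does not settle the matter. A reader might infer that the plan certainly scores non-tumor variants as failures and certainly enrols patients without tumor-derived ctDNA. The documents do not support that; these are possible results of the wording. The defence still leaves the new-mutation clause without a tumor check and the word confirmed undefined.

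Second, the leukocyte statement in Section 6.2.8 concerns germline background, and the endpoint counts somatic mutations. This is correct. The documents neither describe somatic variants of leukocyte origin nor give their frequency, so the size of the effect is assumed. What stands is that the label somatic does not establish tumor origin, and that the tumor match is the only check on origin that the plan describes.

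Third, Cohort D is a descriptive pilot with no success threshold, and a shift of 4 to 12 points lies inside the 25-point half-width. That limits the consequence. But the interval reflects sampling error only and does not reveal a scoring bias.

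Fourth, counting every new mutation is a defensible conservative choice, since a new mutation may be a new tumor clone; Section 6.2.8 values the assay for following acquired resistance. This stands, and it is why unmatched new mutations should not simply be ignored.

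**Conclusion.** The point holds as a gap between a planned step and the endpoint that should use it. The plan calls for tumor confirmation but does not carry it into the clearance definition, and the entry wording leaves open whether a tumor match is needed. Under the literal rule a true rate of 40% would read as 36% to 28% if 10% to 30% of patients were affected independently of tumor clearance. Both the 40% and that range are assumptions. The firm figure is 6.7 points for each patient scored differently.

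Three stronger conclusions are tempting and are not supported:

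- That the bias is only downward. Step 4 of the working shows an upward route.
- That the blood and tumor panels are known to differ in coverage. Section 7.5.2.1.2 does not identify its panel as hotspot.
- That the remedy must be a mandatory tumor match before the first dose, or disregard of every unmatched new mutation. The first could exclude patients with real ctDNA outside the panel's coverage; the second could count a patient with a new tumor clone as cleared.

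This is a change the sponsor should make, with medium confidence, because a fair alternative reading exists.

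**What to change.** In Section 7.5.2.1.2:

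1. Define primary clearance as all baseline blood mutations that are confirmed in the resected tumor being undetectable after 6 doses (week 12).
2. Report the current all-mutation rule as a sensitivity analysis.
3. List new blood mutations not found in the tumor separately, and show the clearance rate with and without counting them as non-clearance.
4. State how blood mutations outside the tumor panel's coverage are classified, and how a treated patient with no confirmed baseline mutation is counted. Otherwise such a patient could meet the new definition by default.

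Reconcile criterion 16 in Section 4.3.1 with Section 4.1.1.3 by stating whether a confirmed positive result means a tumor match.

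The cost is an amendment to one analysis paragraph and a clarification of the entry wording, plus slightly more analysis work. The tumor sequencing is already planned, and Section 6.4.5.3 already makes the resected metastatic tissue the Cohort D baseline specimen. The downside is that some blood mutations may be unclassifiable if the tumor panel proves narrower than the blood assay.

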## 7.5.3 Analysis of Endpoints

## 7.5.3.1 Secondary Endpoints

The secondary endpoints of PFS (cohorts A-C and B) and DFS (cohort D) according to iRECIST 1.1 and OS time will be presented using the Kaplan-Meier method. PFS will be measured in months from the date of first administration of M7824 to the date of documented progression by RECIST 1.1 or death by any cause, whichever is earlier. For Cohort D, DFS will be measured in months from the date of documented recurrence or development of distant metastasis by iRECIST 1.1 criteria. Median PFS and DFS and 95% confidence intervals will be estimated using the Kaplan-Meier method.

OS will be measured in months from the date of first administration of M7824 to the date of death by any cause. Median OS with 95% confidence interval will be estimated using the Kaplan-Meier method. Severity of AEs will be graded using the NCI-CTCAE v4.03 toxicity grading scale. Safety will be assessed by descriptive statistics and summarized in tabular format. This data will be separated based on organ class, immune-relation, severity and relation to M7824.

Adverse events (serious and non-serious) will be considered treatment emergent adverse events when emerging during the on-treatment period defined as the time from first trial drug administration to the last drug administration date + 30 days or the earliest date of subsequent anticancer drug therapy minus 1 day, whichever occurs first, unless otherwise stated. All premature terminations will be summarized by primary reason for treatment withdrawal.

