### **3.2** Secondary Objectives

To estimate progression-free survival (PFS) for M7824 in patients with:

• MSI-H solid tumors whose disease has progressed on prior immune checkpoint blockade therapy (Cohort A-C).

OR

Treatment-refractory, CMS4 mCRC coadministered SBRT (Cohort B). While SBRT is preferred, IMRT or 3D conformal techniques may be utilized at the discretion of the treating radiation oncologist depending on the dose to surrounding normal tissues. Patient will receive a total dose of 24Gy over three days with one of the following modalities, at the discretion of the treating radiation oncologist: SBRT, IMRT and 3D conformal.

To estimate overall survival (OS) for M7824 in patients with:

• MSI-H solid tumors who are refractory to prior immune checkpoint blockade therapy (Cohort A-C).

OR

Treatment-refractory, CMS4 mCRC coadministered SBRT (Cohort B). While SBRT is preferred, IMRT or 3D conformal techniques may be utilized at the discretion of the treating radiation oncologist depending on the dose to surrounding normal tissues. Patient will receive a total dose of 24Gy over three days with one of the following modalities, at the discretion of the treating radiation oncologist: SBRT, IMRT and 3D conformal.

OR

ctDNA(+) resected mCRC following completion of standard-of-care therapy (Cohort D).

To estimate disease-free survival (DFS) in patients with resected mCRC following standard-of-care treatment (cohort D).

To evaluate safety and tolerability of treatment with M7824 in patients with:

• MSI-H mCRC who are refractory to prior immune checkpoint blockade therapy (Cohort A-C).

OR

• Treatment-refractory, CMS4 mCRC (Cohort B)

OR

.

ctDNA(+) resected mCRC following completion of standard-of-care therapy (Cohort D).

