### 7.5 Description of Statistical Analyses

#### 7.5.1 General Considerations

All data recorded during the study will be presented in individual data listings performed on the Safety Analysis Set. All data will be evaluated as observed, and no imputation method for missing values will be used. All data will be presented in a descriptive manner. Each cohort will be analyzed separately, and no multiplicity adjustment across cohorts will be performed.

Descriptive statistics will be used to summarize the trial results, that is, statistics for continuous variables may include means, medians, ranges, and appropriate measures of variability. Categorical variables will be summarized by counts and percentages. The uncertainty of estimates will be assessed by confidence intervals. Unless otherwise specified, the calculation of proportions

will be based on the sample size of the analysis set of interest. Counts of missing observations will be included in the denominator and presented as a separate category.

All other statistical analyses will be performed using SAS® Version 9.1.3 or higher, or R, Version 2.10.1 or higher.

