## 7.5.3.2 Exploratory Endpoints

Summary statistics will be tabulated for microsatellite instability, CMS1, CIMP, KRAS and BRAF status. Paired t-test or Wilcoxon signed rank test will be used to assess the changes in biomarkers pre- and post-treatment. The differences in biomarker levels between responders and non-responders will be assessed using  $X^2$  or Fisher's exact test as appropriate. Similar analysis will be used to assess the correlation between biomarker mutation statuses.

Statistical analyses will be conducted by MDACC statisticians. Tabulations will be produced for appropriate demographic, baseline, efficacy and safety parameters. For categorical variables, summary tabulations of the number and percentage of subjects within each category (with a category for missing data) of the parameter will be presented, as well as two-sided 95% confidence intervals, unless otherwise stated. For continuous variables, the number of subjects, mean, median, standard deviation (SD), minimum, and maximum values will be presented. Time-to-event data will be summarized using Kaplan-Meier methodology using 25th, 50th (median), and 75th percentiles with associated 2-sided 95% confidence intervals, as well as percentage of censored observations.

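### The only Cohort D disease-free survival rule starts the clock at the recurrence, gives no end date and does not count death

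*Combined protocol and SAP*

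**What the plan says.** Section 7.5.3.1 (Secondary Endpoints) gives one sentence on how DFS is timed: "For Cohort D, DFS will be measured in months from the date of documented recurrence or development of distant metastasis by iRECIST 1.1 criteria".

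The two neighbouring rules in that section are complete. For PFS: "PFS will be measured in months from the date of first administration of M7824 to the date of documented progression", with death from any cause as the alternative event, whichever comes first. For OS: "OS will be measured in months from the date of first administration of M7824 to the date of death by any cause".

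The section then commits to an analysis: "Median PFS and DFS and 95% confidence intervals will be estimated using the Kaplan-Meier method". Section 7.5.3.2 adds that time-to-event data are summarised by the 25th, 50th and 75th percentiles with two-sided 95% confidence intervals, "as well as percentage of censored observations".

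DFS is mentioned in only three other places. The list of abbreviations expands the term, section 3.2 names its estimation in Cohort D as a secondary objective, and section 7.3.2 lists it as a secondary endpoint. None of them defines it.

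**The concern.** A time-to-event endpoint needs an origin, a set of events and a rule for patients without an event. The DFS sentence puts the event where the origin belongs, states no end, and names recurrence and distant metastasis but not death.

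Sections 3.2 and 7.5.3.1 assign PFS to Cohorts A-C and B, so DFS is Cohort D's only time-to-event endpoint based on recurrence. Two analysts could repair the sentence differently and report different DFS curves from the same 15 patients. In an open, single-arm cohort, that choice could also be made after the outcomes are known.

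**Working it through.** **1. Is there a DFS figure to reproduce?** No. The plan states no event count, rate or power for DFS. Its only precision figure for Cohort D (section 7.1.3, half-width at most 0.253) reproduces as 1.96 × √(0.25/15) = 0.253, but it concerns the ctDNA clearance rate.

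**2. The three rules side by side (section 7.5.3.1).**

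| Endpoint | Starts | Ends | Death an event? |
|---|---|---|---|
| PFS | first M7824 dose | documented progression or death | yes |
| OS | first M7824 dose | death | yes |
| DFS (Cohort D) | recurrence or distant metastasis | not stated | not listed |

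**3. The DFS rule applied literally.**

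| Patient | Start | End | DFS time |
|---|---|---|---|
| Recurs | recurrence date | none | none |
| Dies without recurrence | none | none | none |
| Neither | none | none | none |

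No patient has a DFS time, so the Kaplan-Meier summaries cannot be formed.

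**4. The likely repair.** Inserting a start at first dose, and making recurrence or metastasis the end, fixes the origin and the end. Death is still not among the listed events, so a patient who dies without recurrence would be censored, contrary to the PFS rule in the preceding sentence.

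**5. What one uncounted death can do.** The input is n = 15 (section 4.1.2.3). The assumptions are no ties, no other censoring, the uncounted death censored at its own rank, and a percentile defined as the first time with S at or below the threshold.

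*All 15 times are events:* S after rank j is (15 − j)/15.
- Rank 4: 11/15 = 0.733, so the 25th percentile is the 4th time.
- Rank 8: 7/15 = 0.467, so the median is the 8th time.

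*The time at rank k is censored instead:* for j > k, S = [(16 − k)/15] × [(15 − j)/(15 − k)].
- 25th percentile, k = 1 to 4: it moves to the 5th time. At k = 1, S there is 10/14 = 0.714; at k = 4, it is 12/15 × 10/11 = 0.727.
- Median, k = 2 to 8: it moves to the 9th time. At k = 2, S there is 14/15 × 6/13 = 0.431; at k = 8, it is 8/15 × 6/7 = 0.457. As an example, k = 4 gives 12/15 × 7/11 = 0.509 at rank 8 and 12/15 × 6/11 = 0.436 at rank 9.
- Median, k = 1: S at rank 8 is 7/14 = 0.500 exactly, so the median stays at the 8th time under this convention.
- Median, k above 8: no change.

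Under last-assessment censoring, the censoring time could precede the death by up to about one 12-week scan interval (84/30.4375 = 2.8 months) while scans continue.

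**6. Scale in months, illustration only.** Assume constant hazards, a median of m months for recurrence with deaths censored, and a share f of first events that are deaths. The recurrence hazard is ln 2/m and the total hazard is that divided by (1 − f), so the median with death counted is m(1 − f). None of these inputs is in the plan.

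| m | f = 0.05 | f = 0.10 | f = 0.20 |
|---|---|---|---|
| 6 | 5.7 | 5.4 | 4.8 |
| 12 | 11.4 | 10.8 | 9.6 |

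**The case against.** The strongest reply is that this is a drafting slip with an obvious repair. The sentence is visibly incomplete and is silent on death rather than excluding it, so the lost words may have included death, as the PFS sentence does. The effect is also conditional: a late death, or none before recurrence, leaves the median where it was. And the plan states that "All data will be presented in a descriptive manner", so no test or decision rests on DFS.

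Much of this stands. The sponsor's intent on death is unknown, the upward shift is conditional, and the stakes are small. It does not remove the defect. No other section supplies the missing words. The events that are listed do not include death, so the smallest repair still omits it. The origin is not beyond doubt either: first dose matches PFS and OS, but the plan does not say so for DFS in this resected cohort.

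Two other provisions help only partly. Section 4.1.5.3 fixes data cut-offs for Cohort D, and section 6.1.4.2 fixes the end of survival follow-up. These bound observation but do not say when an individual patient without an event is censored.

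**Conclusion.** The concern holds. The only DFS rule is wrong as written and cannot produce the results that sections 7.5.3.1 and 7.5.3.2 require. If only a start and an end date are restored, deaths without recurrence would be censored, and the DFS estimate would be higher or unchanged compared with counting them.

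The size in months cannot be derived from the plan. Under the n = 15 assumptions above, one early uncounted death moves the 25th percentile or the median by one ordered time; with no death before recurrence the shift is zero.

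The damage is confined to a descriptive secondary endpoint in a 15-patient pilot cohort. Primary endpoints, sample sizes and stopping rules are untouched. It should be corrected before DFS is analysed, but it does not threaten the trial.

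**What to change.** Replace the DFS sentence in section 7.5.3.1 with a full definition. For Cohort D, DFS is the time in months from first M7824 dose to the earliest of recurrence or distant metastasis (by iRECIST 1.1) or death from any cause. Patients with none of these are censored at their last disease assessment. If the sponsor intends a different origin, that origin should be written in instead.

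The cost is one sentence and no new data. Cohort D is already scanned every 12 weeks (Table 3, footnote k), and section 6.1.4.2 provides post-treatment scans and survival follow-up.

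These smaller points can be settled in the same edit; the conclusion does not depend on them:
- State per-patient censoring dates for PFS and OS too, since the percentage censored is to be reported.
- The PFS sentence cites RECIST 1.1, whereas section 7.3.2 cites iRECIST 1.1; align them.
- Section 4.1.1.3 recognises clinical as well as radiographic recurrence. Say whether a clinical-only recurrence is a DFS event.
- Section 6.1.4.2 continues scans until progression, while the long-term imaging entry in Table 3, as extracted, carries a footnote limiting it to one year after treatment stops. The two need reconciling because they affect the date of last assessment.
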